**14.3.1.3.2. Intercurrent event: Off-protocol lumbar punctures**

As discussed above, LPs are a material and widespread intervention in the treatment of IIH, given with the intention of reducing intracranial pressure and improving the associated symptoms of the disease, including reducing pressure on the optic nerve and papilloedema. Patients that have LPs are expected to experience less pressure on the optic nerve and therefore relatively less papilloedema. Beneficial effects dissipate with time and whilst there has been no longitudinal assessment to quantify papilloedema after an LP the consensus of clinicians would predict that effects of the LP on papilloedema would have dissipated by one month. Outcomes from patients that have undergone off-protocol LPs will confound the estimation of the causal treatment effect of Presendin. OCT outcomes will be recorded repeatedly during the trial. For the reasons stated, we propose to remove OCT outcomes recorded in the 4-weeks following an off-protocol LP, and replace these observations with patient-within-arm imputations generated by a method suitable for longitudinal data imputation.

**14.3.1.3.3. Intercurrent event: Dramatic weight-loss**

Research has shown that weight loss in IIH is associated with reductions in IIH symptoms, including decreases in papilloedema [Sinclair, 2010]. Sudden dramatic weight loss, e.g. arising from a surgical procedure will likely yield material changes to IIH symptoms. This will confound the estimation of the causal treatment effect of Presendin. For these reasons, we propose to remove OCT outcomes of patients that experience weight loss exceeding 10% of baseline weight after a surgical weight-loss procedure from

Study Number: INVEX-CLIN-IIH-301 Protocol	Compound No.: Presendin
	Version: 5.0 for EU countries dated 08Dec2022

the date of procedure. These outcomes will be replaced with patient-within-arm imputations generated by a method suitable for longitudinal data imputation.

#### **14.3.1.4. Outcome: Monthly headache days (MHD)**

##### **14.3.1.4.1. Intercurrent event: Headache-preventative medications**

The great majority of patients are expected to suffer from headache because it is a common symptom of the disease [Wall, 2014; Ottridge, 2017; Markey, 2020]. If a patient takes medication that is intended to prevent headache, it is logical to expect that their headache burden will be decreased. Despite the widely-observed short-term placebo-effect observed in headache outcomes, we expect headache-preventative medication use to be greater in the placebo arm. Outcomes from patients that take headache-preventative medications will confound the estimation of the causal treatment effect of Presendin (more so with botulinum toxin A and CGRP therapies). For these reasons, we propose to remove the headache outcomes following the administration of headache-preventative medications and replace these observations with imputations generated by a method suitable for longitudinal data imputation. This will allow estimation of the treatment effect that is purely and causally attributable to Presendin. Patients who require a change to their headache preventative medications will do this through consultation with the IAC and such a change would be regarded as headache rescue therapy.

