28. Is pregnant or breastfeeding

Note: Use of headache preventative medication is allowed at enrolment (except for Topiramate). Changes to headache preventative medication during the trial should be made in consultation with the IAC – see section [10.1.2](#)

Study Number: INVEX-CLIN-IIH-301 Protocol	Compound No.: Presendin
	Version: 5.0 for EU countries dated 08Dec2022

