#### 6.3.3.1. Headache Preventative Medication Review

A review of any headache preventative medications taken by the patient will be undertaken at each clinic visit. If the Investigator alters the headache preventative medication, this will be considered rescue medication (Section 10.1.1) and the IAC consulted. Use of headache preventative medication will be recorded at trial visits as outlined in the Time and Events table (Table 1).

Study Number: INVEX-CLIN-IIH-301 Protocol	Compound No.: Presendin
	Version: 5.0 for EU countries dated 08Dec2022

Patients will record their acute headache analgesic use in their trial diary.

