## 11.2. Prohibited Medications

### 11.2.1. Prior to screening and randomisation

- Treatment to lower ICP within 1 week prior to screening (e.g., acetazolamide, topiramate (including if used as a migraine preventative), diuretics, glucocorticoids (I.V., injectable steroids or oral (including dexamethasone and prednisolone)). (Nasal, inhaled, or topical steroids are allowed).
- Exposure to fluoroquinolones, lithium, vitamin A, or tetracyclines within 2 months of diagnostic LP
- Glucagon like peptide-1 receptor agonist within last 4 weeks prior to screening
- Warfarin
- Glucose-lowering medication COVID-19 vaccine within 2 weeks prior to screening
- Recreational or illicit drugs during screening period

Note: Use of headache preventative medication is allowed at enrolment (except for Topiramate). Changes to headache preventative medication during the trial should be made in consultation with the IAC – see section [10.1.2](#).

Study Number: INVEX-CLIN-IIH-301 Protocol	Compound No.: Presendin
	Version: 5.0 for EU countries dated 08Dec2022

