### **14.3. Data Analysis Considerations**

#### **14.3.1. Estimands**

We have specified intercurrent events that are material to the measurement of our primary and secondary outcomes, and unbiased estimation of treatment effects attributable to Presendin.

ICP-lowering medication include: acetazolamide, topiramate, diuretics, glucocorticoids (oral dexamethasone and oral prednisolone). Headache-preventative medications include: amitriptyline, topiramate, nortriptyline, beta blockers, candesartan, sodium valproate, pizotifen, botox, CGRP-therapy.

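### The trigger for removing headache data is use of a preventative, not starting or altering one after randomisation, although preventatives are allowed at entry

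*Protocol*

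**What the plan says.** Section numbers are those of protocol version 5.0.

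- **Removal rule (14.3.1.4.1).** "we propose to remove the headache outcomes following the administration of headache-preventative medications"; the removed values are replaced by longitudinal imputation. The stated reason is equally broad: "Outcomes from patients that take headache-preventative medications will confound the estimation of the causal treatment effect of Presendin".
- **Drugs covered (14.3.1).** The list of headache preventatives is "amitriptyline, topiramate, nortriptyline, beta blockers, candesartan, sodium valproate, pizotifen, botox, CGRP-therapy".
- **Entry (note to 5.2.2, repeated in the protocol summary and in 11.2.1).** "Use of headache preventative medication is allowed at enrolment (except for Topiramate"). The same note adds: "Changes to headache preventative medication during the trial should be made in consultation with the IAC".
- **What counts as headache rescue.** 14.3.1.4.1 ends by saying of a change in preventative that "such a change would be regarded as headache rescue therapy". Section 6.3.3.1 says: "If the Investigator alters the headache preventative medication, this will be considered rescue medication". Sections 10.2.1 and 11.2.2 also speak of the investigator altering the drug.

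Version 4.0, bound in the same file, has the same rule (13.3.1.4.1) and the same entry permission.

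**The concern.** An intercurrent event happens after randomisation. A preventative that a patient already takes at entry and continues unchanged is a baseline characteristic. The removal sentence does not separate the two, because its trigger is administration of the drug. Such a patient takes the drug from the start of treatment, so every post-baseline headache value comes after an administration.

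The data at stake are observed and usable. For such a patient the screening diary and the later diaries are both recorded on the same preventative, and use before randomisation cannot be a consequence of the allocated treatment. Replacing these values by imputations would discard information on monthly headache days and on the headache endpoints built from the same diary. The estimate would then be driven by patients who entered without a preventative. Two analysts working from this text could also build different analysis datasets, which a pre-specified rule should prevent.

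**Working it through.** The protocol states no figure on this point, so the check is a comparison of the sections, followed by a sense of scale.

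**1. Does anything in the rule limit it to new use?** No. The removal sentence does not mention starting, changing or randomisation. The sentence giving the reason refers to patients who take these drugs. There is also no end date; the neighbouring rule for off-protocol lumbar punctures (14.3.1.4.2) removes only four weeks of data.

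**2. Can a patient be on a listed drug at randomisation?** Yes, on any of them except topiramate (5.2.2, 11.2.1). No period on a stable dose is required.

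**3. Does other text limit the rule?** Sections 6.3.3.1, 10.2.1, 11.2.2 and the last sentence of 14.3.1.4.1 define rescue through a change or alteration. None of them says that only such a change triggers removal.

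**4. Does the cross-reference help?** No. The notes in the summary, 5.2.2 and 11.2.1 send the reader to 10.1.2 for changes in preventatives, as does 11.2.2. In version 5.0 that section is Definite treatment failure. Headache rescue is in 10.2.1, which does not limit the removal rule either. In version 4.0 section 10.1.2 was the rescue section, so the reference was not updated when the sections were renumbered.

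**5. Why does similar wording work elsewhere?** The rules for ICP-lowering drugs (14.3.1.2.1, 14.3.1.3.1, 14.3.1.4.4) use the same trigger. Those drugs are excluded in the week before screening (5.2.2) and prohibited during the trial (11.2.2), so administration during the trial is new use. Headache preventatives are allowed at entry, so the same wording no longer identifies a post-randomisation event.

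**6. What would replace the data?** Under 14.3.6, repeated measures are imputed from the stratification variables, treatment arm, baseline value and earlier values of the outcome, including imputed ones. A patient with no retained post-baseline value is therefore imputed from arm, strata, baseline and values that were themselves imputed.

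**7. Scale.** The share on a preventative at entry is not given, so a range is assumed. Patients affected under the literal rule = 240 × share. If these patients add almost no information on the treatment effect and the share is equal in both arms, variance rises by about 1/(1 − share).

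| Assumed share | Patients affected | Variance ratio |
|---|---|---|
| 10% | 240 × 0.10 = 24 | 1/0.90 = 1.11 |
| 20% | 240 × 0.20 = 48 | 1/0.80 = 1.25 |
| 40% | 240 × 0.40 = 96 | 1/0.60 = 1.67 |

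If only a start or alteration after randomisation triggers removal, none of these patients loses data unless the preventative changes. The table illustrates the gap between the two readings and is not an estimate of harm.

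**The case against.** The best reply is that nobody would apply the rule literally. It stands under an intercurrent-event heading. It is justified by an expectation of more preventative use in the placebo arm, which makes sense only for use begun or altered after randomisation, since randomisation balances entry use in expectation. The paragraph closes by describing a change as rescue, and three other sections say the same. The parallel rules for ICP-lowering drugs plainly mean starting rescue treatment. The protocol also words the rule as a proposal and leaves estimand and imputation details to the SAP, which is not shown.

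Most of this stands as evidence of intent. It does not repair the wording, because neither the operative sentence nor its stated reason carries the limit. An SAP that follows the protocol inherits the problem, and one that narrows the trigger departs from the protocol.

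A reader might infer that a beta blocker or candesartan taken for blood pressure would also trigger removal, since 14.3.1 lists both without an indication. The documents do not support that: 14.3.1.4.1 concerns drugs taken with the aim of preventing headache, antihypertensives are not among the relevant medications listed in 6.2.1.3, and 11.1 records the reason for each drug.

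**Conclusion.** The concern holds as a wording error with two readings. Read literally, the rule removes all post-baseline headache data from patients who continue an entry preventative unchanged. Read with the surrounding text, it removes data only after a start or alteration. A reader might infer that the sponsor plans to discard these patients' data; the context described above points the other way.

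The reach is limited to the diary-based headache endpoints, which are secondary or exploratory and, by section 4.1.1, not explicitly powered. The patient-reported headache questionnaire is analysed as observed (14.3.5). The primary endpoint and perimetric mean deviation are unaffected. The number of patients affected cannot be derived from the protocol, so the counts and variance ratios rest wholly on the assumed shares. The correction is still worth making before the SAP is final, because the literal rule gives a worse analysis for no stated benefit.

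**What to change.** 1. In 14.3.1.4.1, define the intercurrent event as starting or altering a headache-preventative medication after randomisation. Using altering keeps the analysis rule in line with 6.3.3.1, 10.2.1 and 11.2.2. A list restricted to starts, dose increases and switches would be narrower than those sections, which also cover stopping or reducing a drug, and would create a new mismatch.
2. State that a preventative continued unchanged from entry does not trigger removal.
3. Correct the references to 10.1.2 for headache preventatives so that they point to 10.2.1. The reference in 6.3.3.1 to 10.1.1, now Possible treatment failure, needs the same correction.

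Adjusting the headache models for preventative use at entry is an optional choice for the SAP and is not needed to resolve this point.

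The cost is a sentence or two and the corrected references. No new data are needed: preventative use is reviewed from screening onward (Table 1), and start date, dose and reason are recorded (11.1).

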##### **14.3.1.4.2. Intercurrent event: Off-protocol lumbar punctures**

As discussed above, LPs are a material and widespread intervention in the treatment of IIH, given with the intention of reducing intracranial pressure and improving the associated symptoms of the disease, including reducing the frequency and intensity of headache. Beneficial effects dissipate with time. Prospective data documents alterations in headache for at least 7 days and whilst there is no prospective longitudinal data over a longer time period consensus amongst clinicians would widely acknowledge that headache in some individuals can be influenced for up to a month [Yiangou, 2019]. Outcomes from patients that have undergone off-protocol LPs will confound the estimation of the causal treatment effect of Presendin. MHD outcomes will be recorded daily via diaries. For the reasons stated, we propose to remove MHD outcomes recorded in the 4-weeks following each off-protocol LP and replace these observations with patient-within-arm imputations generated by a method suitable for longitudinal data imputation.

##### **14.3.1.4.3. Intercurrent event: Dramatic weight-loss**

Research has shown that weight loss in IIH is associated with reductions in IIH symptoms, including decreases in headache frequency and severity [Sinclair, 2010].

Study Number: INVEX-CLIN-IIH-301 Protocol	Compound No.: Presendin
	Version: 5.0 for EU countries dated 08Dec2022

Sudden dramatic weight loss, e.g. arising from a surgical procedure will likely yield material changes to IHH symptoms. This will confound the estimation of the causal treatment effect of Presendin. For these reasons, we propose to remove MHD outcomes of patients that experience weight loss exceeding 10% of baseline weight after a surgical weight-loss procedure from the date of procedure. These outcomes will be replaced with patient-within-arm imputations generated by a method suitable for longitudinal data imputation.

#### **14.3.1.4.4. Intercurrent event: ICP-lowering medications**

All patients are expected to suffer from some visual field loss at enrolment because it is the hallmark feature of the disease [Wall, 2014; Ottridge, 2017; Markey, 2020]. If a patient takes ICP-lowering medication, it is logical to expect that their ICP will decrease and that headache will reduce as a result. As stated, we expect ICP-lowering medication use to be greater in the placebo arm. Outcomes from patients that take these medications will confound the estimation of the causal treatment effect of Presendin. For these reasons, we propose to remove the MHD outcomes following the administration of ICP-lowering medications and replace these observations with imputations generated by a method suitable for longitudinal data imputation. Outcomes recorded at the unscheduled visit when the treatment failure is confirmed (and just prior to starting ICP lowering medication) will be defined as the last analysed visit. This will allow estimation of the treatment effect that is purely and causally attributable to Presendin.

#### **14.3.1.5. Primary Estimand (Hypothetical assuming no concurrent procedures, irrespective of adherence to treatment)**

The primary estimand is defined as the following for the primary endpoint:

- Treatment difference in ICP measurement between Presendin and placebo at Week 24 for all patients who are randomised and start treatment, regardless of adherence to randomised treatment, where patients did not have medications or procedures likely to materially affect ICP.

The primary estimand for the initial secondary endpoint will be handled similarly to the primary endpoint using the “Hypothetical” approach. The initial secondary endpoint is defined as:

- Treatment difference in PMD between Presendin and placebo over 24-weeks for all patients who are randomised and start treatment, regardless of adherence to randomised treatment, where patients did not have medications or procedures likely to materially affect PMD.

Study Number: INVEX-CLIN-IIH-301 Protocol	Compound No.: Presendin
	Version: 5.0 for EU countries dated 08Dec2022

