#### 3.2. Secondary Endpoints

- Perimetric Mean Deviation
- Retinal nerve fibre layer (RNFL) thickness
- Optic nerve head size
- The number of monthly headache days (MHD). Monthly headache days will include all headache days, defined as those with an onset, continuation or recurrence, any severity or phenotype of headache, lasting at least 30 minutes or which require acute headache analgesia.
- Number of monthly moderate to severe headache days. A moderate/severe headache day will be defined as a day with moderate or severe pain that lasts at least 4 hours or that requires acute headache analgesic medications
- Responder rate monthly headache days (defined as a  $\geq 50\%$  reduction)
- Responder rate moderate to severe monthly headache days (defined as a  $\geq 50\%$  reduction)
- Headache severity (assessed by 11-point Numeric Rating Scale [NRS], 0-10 where 0 = no pain and 10 = most severe pain)
- Use of acute headache analgesic medications (acute headache analgesics in days per month)
- Visual acuity, as measured by logarithm of the minimum angle or resolution (LogMAR) units
- Treatment failure, defined as initiation of either medical therapy or a surgical intervention to lower ICP.\*

\*criteria defined in rescue therapy section [10.1.1](#)

Study Number: INVEX-CLIN-IIH-301 Protocol	Compound No.: Presendin
	Version: 5.0 for EU countries dated 08Dec2022

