### 14.2. Trial Design Considerations

#### 14.2.1. Sample Size Assumptions

The target sample size for the trial is 240 randomised patients, i.e., 120 patients per arm. We justify this figure in the following sections. The two outcomes for which we sought to power the study are ICP and PMD.

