#### **14.2.1.1. Perimetric Mean Deviation Power**

We summarise here the estimated power for detecting differences between arms in the PMD outcome measure. In the NORDIC trial [Wall, 2014], the authors observed that the improvement from baseline to 6-months in PMD was 0.71dB greater in the experimental arm than the control arm. Cross-sectional SD of PMD was 1.1-1.2 at baseline. Table 2 in their publication shows that the standard error of mean PMD is higher at 6m than at baseline, likely reflecting a combined effect of missing data at 6-months and greater variability of post-baseline measures. We plan to take repeated measures of PMD at baseline, 2 weeks, 1-month (m), 2m, 3 m, 4m, 5m and 6m. Assuming that the overall SD of PMD scores is 1.8, thus introducing some reasonable inflation on Wall *et al.*'s baseline variability parameter for the reasons identified, using the formula given on p.31 of Diggle, Liang & Zeger (1994) we would expect to require 142 patients in total to detect a difference of 0.71dB (justified below) with 90% power at a 5% significance level, if the serial correlation between repeated measures is 0.4 (and we expect a value in this region) [Diggle, 1994]. If the serial correlation parameter is as low as 0.3, the required sample size increases to 166.

Study Number: INVEX-CLIN-IIH-301 Protocol	Compound No.: Presendin
	Version: 5.0 for EU countries dated 08Dec2022

Note that the method used above assumes full follow-up and data collection. Although every effort will be made to collect all outcomes, naturally some missing data is expected. If we inflate the maximum sample size identified above by up to 30% to account for some data loss, we require up to  $166 / 0.7 = 237$  patients. The assumed 30% missing data rate was adjudged to be realistic by the Sponsor based on previous trials in IIH. Thus, we expect to be able to cover the impact of missing data using the extra patients necessitated by the sample size calculation for ICP.

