The above assumes only one eye is measured per patient. In actuality, some patients may provide outcomes for both eyes because any eye that satisfies the eligibility criteria (see Section 5.2) will be enlisted in the study. Put another way, all patients will provide outcomes in at least one eye, and some will provide outcomes in two. Second eyes will naturally be highly correlated with first eyes. From a sample size perspective, this means the additional information in second eyes will be of modest value. Nevertheless, outcomes on second eyes will contain some additional information and should be included in the analysis in the interest of efficiency. When estimating sample size, for the sake of simplicity and because of uncertainty in the rate of eligibility in second eyes, we have assumed that each patient yields outcomes from only one eye. Eligible second eyes will be included in the analysis with appropriate model terms to handle the within-patient correlation (further details are included in the SAP). As such we expect outcomes from second eyes to provide a modest uplift in power to the scenarios presented here.

This section assumes a longitudinal analysis method such as hierarchical regression.

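### The stated PMD sample sizes give 90% power only for a linear slope tested one-sided at 5%, and the protocol states neither; the PMD estimand names no contrast

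*Protocol*

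**What the plan says.** Protocol 14.2.1 states: "The two outcomes for which we sought to power the study are ICP and PMD". Four places then bear on what the PMD comparison is.

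- **Endpoint list (3.2):** the entry is just "Perimetric Mean Deviation", with no time point or summary measure.
- **Estimand (14.3.1.5, same phrase in 14.3.1.6):** "Treatment difference in PMD between Presendin and placebo over 24-weeks for all patients who are randomised and start treatment". The ICP estimand in the same section is tied to a time point: "Treatment difference in ICP measurement between Presendin and placebo at Week 24 for all patients who are randomised and start treatment".
- **Effect size (14.2.1.1, Perimetric Mean Deviation Power):** taken from an earlier trial in which "improvement from baseline to 6-months in PMD was 0.71dB greater in the experimental arm than the control arm".
- **Sample size (same section):** with SD 1.8 and eight measurement occasions, a cited textbook formula that is not written out gives "142 patients in total to detect a difference of 0.71dB (justified below) with 90% power at a 5% significance level" at correlation 0.4. Then: "If the serial correlation parameter is as low as 0.3, the required sample size increases to 166". Dividing 166 by 0.7 gives 237, which is said to cover 30% data loss within the 240 randomised.

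On the analysis behind the power, the section says only: "This section assumes a longitudinal analysis method such as hierarchical regression". Sidedness is not stated for PMD. The one hypothesis in 14.1, for ICP, has a two-sided alternative. Version 4.0, bound in the same file, has the same PMD wording and figures in its Section 13.

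**The concern.** A power statement means something only for a named contrast and a named error rate. Here the effect is a difference at one time point, the estimand covers a period, and the calculation uses a formula the reader cannot see. A slope, an average over visits and a Week 24 difference need different numbers of patients and can lead to different conclusions from the same data.

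The way N moves with the correlation shows the mismatch. For an average over visits, N falls as the correlation falls. The protocol's N rises, and 166/142 = 1.169 is almost exactly (1 − 0.3)/(1 − 0.4) = 1.167. So the powered contrast has variance proportional to 1 − ρ, and no section names such a contrast. If the 90% depends on unstated choices, the sponsor may be relying on more power for its second powered outcome than the design gives.

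**Working it through.** **Inputs (Protocol 14.2.1 and 14.2.1.1).** Difference 0.71 dB; SD σ = 1.8 (σ² = 3.24); ρ = 0.4 or 0.3; times 0, 0.5, 1, 2, 3, 4, 5, 6 months; 90% power; 5% level; 1:1 allocation. My assumptions: exchangeable correlation, equal SD in both arms, normal approximation, one eye per patient.

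Let K = (z_α + z_power)². One-sided 5%: (1.645 + 1.282)² = 8.564. Two-sided 5%: (1.960 + 1.282)² = 10.507.

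**Step 1: reproduce 142 and 166.** For a difference in linear slopes, the number per arm is m = 2Kσ²(1 − ρ)/(Sxx·b²). Here b = 0.71/6 = 0.1183 dB per month, Sxx = 33.47 for the eight times, and Sxx·b² = 0.4687.

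- One-sided, ρ = 0.4: 2 × 8.564 × 3.24 × 0.6/0.4687 = 71.05 per arm, total 142.1.
- One-sided, ρ = 0.3: 2 × 8.564 × 3.24 × 0.7/0.4687 = 82.89 per arm, total 165.8.

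Both match the protocol to the nearest patient.

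**Step 2: try the alternatives.** Total N for 90% power, unrounded per arm, at ρ = 0.4 / 0.3:

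| Contrast | Variance factor | One-sided 5% | Two-sided 5% |
|---|---|---|---|
| Slope | (1 − ρ), with Sxx and b | 142 / 166 | 174 / 203 |
| Week 24, baseline-adjusted | 1 − ρ² | 185 / 200 | 227 / 246 |
| Change score, baseline to 6 months | 2(1 − ρ) | 264 / 308 | 324 / 378 |
| Average of 7 post-baseline visits, constant 0.71 dB | (1 + 6ρ)/7 | 107 / 88 | 131 / 108 |

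The last three rows use N = 4Kσ² × factor/0.71². Only the one-sided slope gives both stated figures.

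**Step 3: power of the stated patients at two-sided 5%.** With 71 per arm at ρ = 0.4 and 83 per arm at ρ = 0.3:

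- Slope: 83% and 83%.
- Week 24, baseline-adjusted: 73% and 76%.

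**Step 4: the allowance for 30% loss.** For the slope at two-sided 5%, 203/0.7 is about 291 at ρ = 0.3, the case behind the protocol's 237. At ρ = 0.4, 174/0.7 is about 249. Both exceed 240.

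**Step 5: split the Week 24 gap.** At ρ = 0.4 the gap is 227 − 142 = 85, of which 185 − 142 = 43 comes from the contrast and 227 − 185 = 42 from sidedness. At ρ = 0.3 it is 246 − 166 = 80, of which 34 comes from the contrast and 46 from sidedness.

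**Step 6: power of the actual design at two-sided 5%, ρ = 0.3 / 0.4.**

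| Contrast | 120 per arm | 83 per arm (166 left after 30% loss) |
|---|---|---|
| Slope | 94% / 97% | 83% / 89% |
| Week 24, baseline-adjusted | 89% / 92% | 76% / 79% |

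**Step 7: dependence on the shape of the effect.** The slope rows assume linear growth to 0.71 dB at 6 months. If 0.71 dB is instead present from the first post-baseline visit and stays flat, slope power at 83 per arm is only 29% / 33%. Conversely, under linear growth the average effect over the seven visits is 0.36 dB, and the baseline-adjusted average has 65% / 63% power.

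**The case against.** The strongest reply is that the passages can be reconciled. A 0.71 dB difference built up from baseline to 6 months is 0.71/6 dB per month. A difference over 24 weeks estimated by hierarchical regression can be read as a treatment-by-time slope, and the numbers reproduce from exactly that slope. This stands. A reader might infer that the stated power cannot belong to the stated estimand, or that the protocol commits to three conflicting contrasts. The text supports neither: it nowhere says average and nowhere says slope. What it supports is that the contrast is unnamed.

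A reader might also take the calculation for a within-patient change comparison, since that variance too scales with 1 − ρ. It is not one: a change score needs 264–378 patients. Nor should the whole distance from 142–166 to 227–246 be put down to the choice of contrast, since about half of it is sidedness.

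The power after 30% loss is also somewhat pessimistic. It treats 30% of patients as contributing nothing, whereas 14.3.6 imputes from earlier observations and 14.2.1.1 expects a modest gain from eligible second eyes.

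Finally, 14.3.1.6 leaves details to the SAP, and the choice of model for a secondary endpoint properly belongs there. That does not answer the point, because the effect size, the patient numbers, the 90% and the 237 are all stated in the protocol. A SAP can choose a contrast, but it cannot make those figures true for it.

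**Conclusion.** Wrong as written. The 90% power at 142 and 166 patients holds only for a linear slope tested one-sided at 5%, and the protocol states neither condition. Read with the two-sided convention of its only stated hypothesis, those numbers give about 83% for the slope and 73–76% for Week 24, and the claim that 237 patients cover 30% loss fails.

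The design itself is not badly short. With all 240 patients, two-sided power is about 94–97% for the slope and 89–92% for Week 24; with 30% contributing nothing it is 83–89% and 76–79%.

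These figures rest on exchangeable correlation of 0.3–0.4, SD 1.8 in both arms, one eye per patient, a normal approximation and, for the slope, linear growth. Identifying the formula as a slope is an inference from matching both figures, since the protocol does not write it out.

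**What to change.** - **14.3.1.5 and 14.3.1.6:** name one PMD contrast. The Week 24 difference in change from baseline fits the 0.71 dB and parallels ICP. A treatment-by-time slope is also acceptable if linearity is stated and justified. The choice is the sponsor's: the slope has more power if the effect grows linearly and much less if it appears early and stays flat.
- **14.2.1.1 (Perimetric Mean Deviation Power):** write out the formula, state the sidedness, and restate N and power for the chosen contrast with and without 30% loss, using the two-sided figures above if the test is two-sided. Correct or remove the statement that 237 patients cover the loss. Note that partial follow-up and second eyes would raise the power somewhat.
- **SAP:** carry the same contrast.

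The cost is a change of wording and a less favourable stated PMD power. No patients or visits are added.
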